1.8 Compliance Statement

This study will be conducted in full accordance of all applicable CHOP Research Policies and Procedures and all applicable federal and state laws and regulations including 45 CFR 46, 21 CFR Parts 50, 54, 56, 312, and the Good Clinical Practice (GCP): Consolidated Guideline approved by the International Conference on Harmonization (ICH). Adverse event reporting will be targeted, so that potential adverse events arising from the use of inhaled tobramycin (for example, inhalational side-effects as well as renal adverse events) will be reported, while other adverse effects attributed to the underlying disease or clinical care will not be reported. All episodes of noncompliance will be documented.

The investigators will perform the study in accordance with this protocol, will obtain informed consent, and will report unanticipated problems involving risks to subjects or others in accordance with the CHOP IRB Policies and Procedures and all federal requirements. Collection, recording, and reporting of data will be accurate and will ensure the privacy, health, and welfare of research subjects during and after the study.

2 STUDY OBJECTIVES

The objective of this trial is to evaluate the safety and tolerability of tobramycin solution for inhalation in very preterm infants with BPD who have evidence of a pathogenic GNR detected by tracheal aspirate culture.

2.1 Primary Objective

The primary objective of this study is to determine the maximum well-tolerated dose of tobramycin solution for inhalation (selected between 78mg, 150mg, 216mg, and 300mg administered twice daily) administered to very preterm infants with BPD who are actively receiving invasive mechanical ventilation and have evidence of a pathogenic GNR detected by tracheal aspirate culture.

2.2 Secondary Objectives

The secondary, exploratory objectives are to:

• Evaluate the association between the dose of inhaled tobramycin, plasma tobramycin pharmacokinetics, and peak tracheal aspirate tobramycin levels.

- Compare the change (pre vs. post study) in tracheal aspirate pathogenic bacterial colony forming unit (CFU) counts measured by high resolution culture, (1) between participants in the phase 1 trial and untreated infants in the observational cohort, and (2) between trial participants stratified by the administered dose of inhaled tobramycin.
- Compare the longitudinal change in measures of administered respiratory support (FiO₂, ventilator mean airway pressure, and respiratory severity score) during the 14-day study period, (1) between participants in the phase 1 trial and observational cohort and (2) between trial participants stratified by the administered dose of inhaled tobramycin.
- Compare changes (pre vs. post treatment) in tracheal aspirate cytokine levels, neutrophil/WBC ratio, and patterns in the airway microbiome, stratified by the administered dose of inhaled tobramycin.
- Change in the following measures of hypoxemia (SpO₂<80%): Intermittent hypoxemia (events lasting 10s-3min), prolonged hypoxemia (events lasting >1min), and daily proportion of time in hypoxemia
- Compare the longitudinal change in dynamic lung compliance, airway resistance, peak expiratory flow, and CO₂ elimination during the 14-day study period, (1) between participants in the observational cohort and phase 1 trial and (2) between trial participants stratified by the administered dose of inhaled tobramycin.

3 INVESTIGATIONAL PLAN

3.1 General Schema of Study Design

This study is an open-label, phase 1, inter-patient 3+3 dose escalation feasibility trial. A prospective, observational (non-treated) cohort of eligible infants will also be enrolled and outcomes compared to the trial participants. The study phases are depicted in **Figure 6** and described in the sections that follow.

3.1.1 Screening Phase

Potential subjects will be screened using daily census logs and the protocol inclusion and exclusion criteria. Male and female infants who meet the criteria will be eligible to undergo a once-weekly screening tracheal aspirate culture while receiving invasive mechanical ventilation. Infants with a screening culture that is positive for a pathogenic GNR bacteria will become eligible to enroll in the phase 1 trial of inhaled tobramycin or the untreated, observational cohort. Infants must begin the phase 1 trial or observational (non-treated) cohort 14-day study period within 7 days of collection of the screening tracheal aspirate sample that is positive for a pathogenic GNR (**Figure 6**). Infants whose screening culture(s) is/are negative for a pathogenic GNR bacteria will continue to be screened weekly for as long as they meet study eligibility criteria. This plan for serial screening is consistent with the regular surveillance used to monitor for Pseudomonas infection in children with CF and reflects the increasing risk of developing a GNR respiratory infection with longer duration of invasive mechanical ventilation.^{10,71,72}

3.1.2 Phase 1 Trial

The phase 1 trial will last up to 14 days, with each infant receiving an inhalational dose of tobramycin solution administered every 12 hours via vibrating mesh nebulizer. The dose (78mg, 150mg, 216mg, or 300mg) will be determined as per the 3+3 design protocol (**Figure 2**). During the investigational drug trial, each infant will undergo blood and tracheal

aspirate sampling and respiratory mechanics measurements at pre-specified time points to assess dosage safety and potential efficacy. Continuous pulse oximetry will be performed beginning 24-48hr prior to initiating the study drug and continued until completion of the 14-day trial. Review of clinical data and assessment for adverse events will be conducted daily throughout the 14-day trial.

3.1.3 Observational (non-treated) Cohort

Infants enrolled in the observational (non-treated) cohort will undergo 14 days of clinical data collection. During the study phase, respiratory mechanics measurements will be performed on study days 1 and 7. Respiratory mechanics measurements will also be performed \leq 48 hours after the final study day as indicated in section 3.1.4. Pulse oximetry will be performed throughout the 14-day study period.

[figure not shown]

Figure 6. Diagram of study phases. *GNR, Gram-negative rod.* * *Details of both the phase 1 trial and observational (non-treated) cohort will be discussed with eligible families during the consent conversations. Eligible infants may participate in either cohort but can be enrolled in only one cohort. Infants will enter into one of the two study cohorts within 7 days from the collection of the screening tracheal aspirate.*

3.1.4 Follow-up Phase

All enrolled study infants will be followed until hospital discharge with pre-defined clinical data abstracted periodically from the medical record. For infants enrolled in the phase 1 trial, tracheal aspirate samples for microbiology testing and cytokine level measurements will be collected \leq 48 hours and 14 days (or on the day of planned tracheal extubation, if earlier) after receiving the final dose of inhaled tobramycin. For infants enrolled in the observational cohort, a tracheal aspirate for high resolution culture will be collected \leq 48 hours after study day 14. Infants enrolled in both cohorts will undergo the third and final respiratory mechanics measurements \leq 48 hours after the final study day.

3.2 Allocation to Treatment and Masking

Infants who satisfy the inclusion and exclusion criteria and a parent or guardian consents for the infant to participate in the phase 1 trial will be allocated to receive up to 14 days of tobramycin solution for inhalation at the dosage determined by the 3+3 trial design. Drug dosage will not be masked (blinded).

3.3 Study Duration, Enrollment, and Number of Sites

3.3.1 Duration of Study Participation

The study duration for each subject will last from enrollment until hospital discharge. For infants who participate in the phase 1 trial of inhaled tobramycin, the drug trial will last up to 14 days. The last tracheal aspirates obtained for research purposes will be collected up to 14 days after completing the final administered dose of inhaled tobramycin. For infants who participate in the observational (non-treated) cohort, clinical data will be collected daily for 14 days beginning after enrollment. Respiratory mechanics data will be recorded at study entry (day 0 for the trial participants, day 1 for the observational cohort), study day 7, and \leq 48 hours after the final study day.

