Study Phases						
Screening Phase	Potential subjects will be screened using daily census logs and the protocol inclusion and exclusion criteria. Infants who meet study eligibility criteria will be enrolled if a parent or guardian consents to once-weekly collections of a screening tracheal aspirate culture. If a screening culture is positive for a pathogenic GNR, the infant will be eligible to participate in the phase 1 trial or observational (non-treated) cohort, but can be enrolled in only one.					
Study Phase Phase 1 Trial	The phase 1 trial will last up to 14 days, with each infant receiving a specified dose of tobramycin solution for inhalation every 12 hours, administered via vibrating mesh nebulizer. The drug dose (78mg, 150mg, 216mg, or 300mg) will be determined as per the interpatient dose escalation 3+3 design protocol. If the 300mg dose level is completed without evidence of safety concerns (i.e., stopping rules are not met), up to 3 additional infants will be enrolled to receive 300mg to provide a more robust assessment of drug dose tolerability and PK. During the trial, each infant will undergo continuous pulse oximetry, and blood and tracheal aspirate sampling and respiratory mechanics measurements at prespecified time points to assess dose safety and potential efficacy. Clinical data will also be recorded daily throughout the trial.					
Observational (non- treated) Cohort	Infants enrolled in the untreated observational cohort will undergo continuous pulse oximetry for 14 days after enrollment. Respiratory					

	mechanics measurements will be performed at set timepoints. Clinical data will be collected daily from the medical record.							
Follow-Up Phase	All infants enrolled in the phase 1 trial and observational cohorts will be followed until hospital discharge. Pre-defined clinical data will be abstracted periodically from the medical record. For infants enrolled in the phase 1 trial, tracheal aspirate samples for high resolution culture, 16s sequencing, and cytokine level measurement will be collected ≤48 hours and 14 days after receiving the final dose of inhaled tobramycin. Infants enrolled in the observational cohort will undergo tracheal aspirate collection f culture ≤48 hours after completing the 14-day study phase. Infants in both cohorts will undergo respiratory mechanics measurements ≤48 hours after completing the study phase.							

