^a "Day 0" procedures to be completed ≤7 days prior to trial Day 1 ^b "Day 15" procedures to be completed ≤48 hours after the final administered dose of inhaled tobramycin (phase 1 trial) or study day 14 (observational cohort)

° Tracheal aspirate sample collected 14 days after the final administered dose of inhaled tobramycin or on the day of planned tracheal extubation, if earlier

^d Serum magnesium and phosphorus levels will be checked with the comprehensive metabolic panel on trial days 7 and 14.

* Up to 6 blood samples (200µL per sample) for pharmacokinetic analyses (PK) will be collected per infant concurrent with clinically ordered blood draws.

page xvi

[figure not shown]

Figure 1. Study enrollment and phases flow diagram.

* Details of both the phase 1 trial and observational (non-treated) cohort will be discussed with eligible families during the consent conversations. Eligible infants may participate in either cohort but can be enrolled in only one cohort.

page xvii

[figure not shown]

Figure 2. 3+3 dose escalation design schematic. MTD: maximum tolerated dose

Up to 4 different dosages of tobramycin solution for inhalation will be investigated using the above 3+3 trial design (78mg, 150mg, 216mg, and 300mg; all administered every 12 hours for up to 14 days). If the 300mg dose level is completed in 3 participants and none show evidence of a toxic response, up to 3 additional infants will be enrolled to receive to receive 300mg. The trial will be stopped if 2 of the additional infants receiving 300mg develop a toxic response and the 216mg dose will be used as the maximum tolerated dose in subsequent trials.

A toxic response is defined as the occurrence of any of the following safety endpoints during the 14-day phase 1 trial (see individual subject and full study stopping rules in section 5.2.4 and 5.2.5 for more details):

- Trough serum tobramycin level (measured 11 hours after the last administered dose) ≥1µg/mL
- Increase in serum creatinine level by ≥0.3mg/dL above the pre-trial level¹⁻³
- Increase in serum creatinine >1.5-fold above the pre-trial level¹⁻³
- Urine output <0.5mL/kg/hr for 12 hours¹⁻³
- Any serious adverse event possibly attributable to the study drug^b

^b The likelihood an adverse event is attributable to a study intervention will be defined as outlined in section 8.3.

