^a "Day 0" procedures to be completed ≤7 days prior to administration of the first study drug dose. The quantitative tracheal aspirate culture and cell count differential obtained during the screening phase will be used for the laboratory values. Prior to initiating study drug therapy, one additional tracheal aspirate will be collected for cytokine level measurements and 16s sequencing.

^b "Day 15" procedures to be completed ≤48 hours after administration of the last study drug dose

° Follow-up tracheal aspirate for quantitative culture will be collected 14 days after the last administered dose of inhaled tobramycin or on the day of planned tracheal extubation if earlier

^d Tracheal aspirate for tobramycin level measurements obtained on trial day 7 will be collected approximately 1hr, 3hr, 6hr, 9hr, and 11hr after drug administration. Samples collected on trial days 4, 10, and 14 will be collected approximately 11hr after administration of doses number 8, 20 and 28, respectively.

e Serum and blood tobramycin trough levels will be drawn concurrently, 11 hours after administration of the previous dose

^f Blood draws for comprehensive metabolic panels should be bundled with draws for tobramycin trough levels or other clinically ordered blood draws. Comprehensive panel to include a magnesium and phosphorus level on day 7 and 14.

^g Serum and blood tobramycin peak levels will be drawn concurrently, 1 hour after completion of the previous dose

^h Up to 6 blood tobramycin levels per infant will be drawn concurrent with clinically ordered blood draws.

ⁱ Weekly medical record review to assess for adverse events will take place until hospital discharge

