5.1.2 Continuous pulse oximetry

A research pulse oximeter (see section 4.3.4) will be used throughout the 14-day study period to measures reliable SpO_2 levels. Oximeter monitoring will begin 24-48 hours prior beginning the phase 1 drug trial to establish baseline values.

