5.1.6 Respiratory mechanics measurements

A Philips Respironics NM3 respiratory profile monitor will be used to collect respiratory mechanics data. Measurements will be performed at 3 time points: at study entry (study day 0 for infants enrolled in the phase 1 trial, study day 1 for infants enrolled in the observational cohort), study day 7, and \leq 48 hours after completing the 14-day study period. Each recording period will last 4 hours and coincide with a period of quiet sleep. The NM3 monitor is FDA approved for use in infants (510 (k) K091459). The Respironics NM3 monitor will be used to collect data on the following endpoints: dynamic compliance (mL/cm H₂O), peak expiratory flow (L/min), airway resistance (cm H₂O/L/sec), and carbon dioxide elimination (mL/min). These data will be downloaded to a dedicated, password protected study computer following each recording session. For this analysis, only results obtained from mandatory, ventilator driven non-pressure support breaths will be used.

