Tracheal aspirate cytokine levels	Yes	No	 Individual cytokine levels measured pre-trial, ≤48 hours after the final dose, and 14 days after the final drug dose will be summarized. Transformation (e.g. logarithmic) or categorization by centiles will be considered based on the data distribution. Correction for total protein levels in the tracheal aspirate will be employed to account for differences in dilution during sample collection. The relative intra-patient change for the individual cytokine levels 	
			 from pre-trial baseline to the 2 post-trial timepoints will be calculated and compared between dose levels. The association between change in cytokine levels and tobramycin dose will be explored using bivariate and multivariate correlation analyses with Bonferroni correction for multiple testing.¹⁰⁰ We will consider exploratory cluster and linear discriminate analyses to identify airway immunological profiles associated with differences in the response to inhaled tobramycin (e.g. change in CFU/mL).^{101,102} 	
Respiratory support measures Hypoxemia (SpO ₂ <80%)	Yes	Yes	 Continuously recorded FiO₂, MAP, and RSS values will be converted to time-weighted daily averages for each study day. Continuously recorded SpO₂ data will be used to calculate daily rates of intermittent and prolonged hypoxemia and daily total hypoxemia exposure. Assessment of longitudinal change using linear mixed effects models will be considered. 	
Pulmonary mechanics	Yes	Yes	 Infants in both study cohorts will undergo pulmonary mechanics measurements pre-trial, after 7d, and after 14d. Intra-patient change, relative to pre-trial baseline, will be calculated for each participant and compared (1) between the two cohorts and (2) stratified by drug dose. Assessment of longitudinal change using linear mixed effects models will be considered. 	

Table 7. Planned statistical techniques and data availability for the phase 1 trial outcomes

CFU, colony forming units; GNR, Gram-negative rod; TA, tracheal aspirate

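### Baseline lung mechanics may be recorded several days before Day 1 in treated infants but on Day 1 in untreated infants, and the planned between-cohort comparison of change makes no allowance for the unequal interval

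*Combined protocol and SAP*

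**What the plan says.** **Timing of lung mechanics.** Section 3.3.1 sets the schedule: "Respiratory mechanics data will be recorded at study entry (day 0 for the trial participants, day 1 for the observational cohort), study day 7", with a final recording within 48 hours of the end of the study period. Section 4.3.3 repeats the split, and so does section 5.1.6: "study day 0 for infants enrolled in the phase 1 trial, study day 1 for infants enrolled in the observational cohort". For the observational cohort, section 3.1.3 says "respiratory mechanics measurements will be performed on study days 1 and 7"; section 4.2 and Table 1 agree.

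**Width of Day 0.** Tables 1 and 5 both mark trial mechanics on Day 0. Footnote a to Table 1 describes Day 0 as "procedures to be completed ≤7 days prior to trial Day 1", and footnote a to Table 5 as "procedures to be completed ≤7 days prior to administration of the first study drug dose". The observational Day 1 recording has no such window.

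**Planned comparison.** Table 7 says "Infants in both study cohorts will undergo pulmonary mechanics measurements pre-trial, after 7d, and after 14d", then plans to compare each infant's change from pre-trial baseline between the two cohorts and across dose levels.

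**Oximetry.** For the trial, section 5.1.2 says "Oximeter monitoring will begin 24-48 hours prior beginning the phase 1 drug trial to establish baseline values", and sections 3.1.2 and 4.3.4 give the same pre-period. For the observational cohort, the Synopsis says infants "will undergo continuous pulse oximetry for 14 days after enrollment", and section 3.1.3 refers only to the 14-day period. Table 1, however, marks oximetry on Day 0 for that cohort.

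**The concern.** A change score compares like with like only if it spans a similar length of time in each group. Here the later recordings fall on common study days, but the starting point can be earlier in treated infants and cannot be earlier in untreated ones. The timing difference is one-sided.

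The mechanics endpoints are raw values (compliance in mL/cm H2O, flow in L/min, CO2 elimination in mL/min) in infants who are growing and whose lung disease is changing. Anything that happens over the extra pre-treatment days enters the treated cohort's change and would be read alongside any drug effect. Cohorts are not randomised and families may join either one, so common timing is one of the few comparability protections available. Section 5.3 says these data are meant to inform on possible effects of the drug on respiratory function, and section 9.4.3 expects the study to inform phase 2 and 3 design.

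**Working it through.** The documents give no sample size, power or expected effect for lung mechanics, so there is no stated figure to reproduce. The check is calendar arithmetic.

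**1. Interval as a function of the baseline offset.** Let *d* be the number of days the trial baseline precedes Day 1. For observational infants *d* = 0. Counting from Day 1:

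- baseline to Day 7 = 6 + *d* days;
- baseline to final recording = 13 + *d* to 15 + *d* days, for infants who complete 14 days (Day 14 is 13 days after Day 1, plus 0-2 days).

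**2. How large *d* can be.** Footnote a alone allows *d* up to 7. Other rules bind first:

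- Day 1 must fall within 7 days of collection of the positive screening aspirate (section 3.1.1).
- Consent to either cohort is not taken until the culture result is available (section 9.6).
- Consent must precede study procedures (sections 4.1 and 9.6).

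Hence maximum *d* = 7 − (culture turnaround + time to consent), which is below 7. The documents do not give that time. Assuming 1 to 3 days: 7 − 3 = 4 and 7 − 1 = 6, so the ceiling is about 4-6 days.

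**3. Resulting intervals.**

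| *d* (days) | To Day 7, trial | To Day 7, observational | To final, trial | To final, observational |
|---|---|---|---|---|
| 0 | 6 | 6 | 13-15 | 13-15 |
| 1 | 7 | 6 | 14-16 | 13-15 |
| 4 | 10 | 6 | 17-19 | 13-15 |
| 6 | 12 | 6 | 19-21 | 13-15 |

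**4. Illustrative size.** Assume a 3,000 g infant, a gain of 20-30 g/day and compliance proportional to weight; none of these figures is in the documents. Extra change = *d* × daily gain / 3,000:

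- *d* = 1: 20/3,000 = 0.7% to 30/3,000 = 1%;
- *d* = 4: 80/3,000 = 2.7% to 120/3,000 = 4%;
- *d* = 6: 120/3,000 = 4% to 180/3,000 = 6%.

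At the ceiling this is about 3-6%; for a one-day gap it is about 1%.

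**5. Whether the analysis removes it.** Section 6.3.3 starts with paired tests against baseline and non-paired tests between cohorts; neither has a term for elapsed time. Mixed models are only to be considered, and their time variable is treatment week, not days since the baseline recording. Nothing in the plan accounts for the unequal interval.

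**The case against.** A reader might infer from footnote a that the gap can reach a full 7 days: 13 versus 6 days to Day 7, and 22 versus 15 days to the latest final recording. The documents do not support that. The 7-day limit from sample collection and the wait for the culture result before cohort consent rule it out, and the actual offset may be zero.

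A reader might also infer that growth and recovery over the extra days must flatter the drug. That is not shown. Weight, growth rate and scaling are assumptions, and section 6.3.3 itself expects disease acuity to fluctuate. Extra pre-treatment days could include worsening.

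Nor is the oximetry issue the same fault. It is a disagreement of 1-2 days between the text and Table 1, whose Day 0 mark already implies a pre-period for untreated infants. Hypoxemia is summarised as daily rates, and baseline and later values are also to be compared directly between cohorts, so that analysis does not rest on change scores alone. A Day 1 value in an untreated infant is still an unexposed baseline.

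Finally, mechanics is exploratory, the cohorts are non-randomised and ventilator management is not protocolised, so a few days' offset is one limitation among several. This lowers the importance of the point without answering it: the unequal window is written into several sections, Table 7 describes the timing as common to both cohorts, and aligning it is cheap.

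**Conclusion.** The point stands as a modest, correctable design weakness. The baseline-to-measurement interval can be longer only in treated infants, and no planned analysis adjusts for it. The excess ranges from none to about 4-6 days, assuming 1-3 days for culture and consent. Under the stated growth assumptions, the ceiling corresponds to about 3-6% in compliance without drug effect. The direction of any net bias is unknown.

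An earlier baseline in trial infants is not itself wrong, since it must precede the first dose, and a Day 1 baseline in untreated infants is not wrong either. The fault is the unequal window combined with no adjustment. Dose escalation, the stopping rules and the primary safety endpoint do not depend on it. The observational oximetry start is a separate, smaller inconsistency that needs reconciling.

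**What to change.** - **Mechanics.** In sections 3.1.3, 3.3.1, 4.2, 4.3.3 and 5.1.6 and in Tables 1 and 5, give both cohorts the same baseline window, for example within the 24-48 hours before Day 1, and before the first dose in trial infants. Table 7's description of the timing would then be accurate.
- **Leave unchanged** the 7-day window for the screening culture and for the Day 0 aspirate used for cytokines and 16S sequencing. No fault is shown there.
- **Infants already measured under the current windows.** Record the baseline date and use actual days since baseline in the between-cohort mechanics comparison.
- **Oximetry.** Reconcile the Synopsis and section 3.1.3 with Table 1's Day 0 mark, so that both cohorts have the same 24-48 hour pre-period.

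The cost is protocol wording, tighter scheduling of one mechanics session inside the existing 7-day start limit, and 1-2 days of oximetry per untreated infant, which Table 1 already implies. No mechanics recordings are added.
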